Limitations do exist in these studies on Vitamin D level and bronchiectasis. Firstly, the studies beforehand mentioned were conducted among Caucasian and middle-east populations (26-29). It has been well reported that the aetiology of bronchiectasis varies greatly across ethnic groups (14). There is also geographical variation in epidemiology and microbiology of bronchiectasis. Secondly, relatively small sample sizes were used in these prior studies.

Our group is also conducting a prospective clinical study on serum 25-hydroxyvitamin D (25-OH D) level and risk of bronchiectasis exacerbation (UW 22-317) which started in January 2023 and targeted for completion by end of 2024. There were 104 subjects recruited who will be followed up for 12 months. In this ongoing study, 42 (39.3%) of the patients had vitamin D deficiency with baseline vitamin D level below 50 nmol/L. There were 70 patients who completed the interim analysis at 6 months. Patients who are vitamin D deficient had increased risks of developing bronchiectasis exacerbation (10% in Vitamin D deficient group and 0% in vitamin D non-deficient group), p-value = 0.082. Patients who are vitamin D deficient had increased risks of developing hospitalized bronchiectasis exacerbation (13.3% in vitamin D deficient group and 2.5% in vitamin D non-deficient group), p-value = 0.041. Patients with vitamin D deficiency also had higher SGRQ score (symptom domain) [39.4 ± 22.5 vs 28.1 ± 20.4, p = 0.011], SGRQ score (impact domain) [23.6 ± 19.3 vs 16.0 ± 14.9, p = 0.024] and total SGRQ score [29.3 ± 18.1 vs 22.9 ± 15.2, p = 0.063]. The data from this preliminary local pilot data suggested that vitamin D deficiency might have important role in bronchiectasis in terms

of symptom burden and exacerbation risks.

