This study therefore seeks to address the limitations in previous related studies on vitamin D replacement and bronchiectasis exacerbation occurrence through a self-controlled pilot study. We aim to investigate whether vitamin D replacement in bronchiectasis patients with vitamin D deficiency can reduce hospitalized bronchiectasis exacerbation occurrence. Patients who participated in the prior study entitled “Prospective clinical study on serum 25-hydroxyvitamin D (25-OH D) level and risk of bronchiectasis exacerbation” (UW 22-317) will be invited for participation during regular clinic follow-up and management in Queen Mary Hospital. If they are willing to join the further research, they will be recruited in this self-controlled study. There are some differences from usual management to non-CF bronchiectasis subjects. The study subjects would be checked for their blood 25-hydroxyvitamin-D level during the study period. The non-CF bronchiectasis subjects with Vitamin D deficiency would be given 1000 IU and 2000 IU (if needed). We aim to correct their Vitamin D deficiency completely, aiming at blood 25-hydroxyvitamin-D level $>= 50$, i.e. treat to target. The dose depends on the level of Vitamin D after replacement. If blood 25-hydroxyvitamin-D level is 50 or above, then 1000 IU is suffice. If blood 25-hydroxyvitamin-D level is still below 50, we will increase to 2000 IU.

4. Hypothesis

We hypothesize that replacing vitamin D to raise the blood 25-hydroxyvitamin-D level above 50 nmol/L can reduce the occurrence of hospitalized bronchiectasis exacerbation among patients with bronchiectasis and baseline vitamin D deficiency.

5. Objectives

To investigate whether vitamin D replacement in bronchiectasis patients with vitamin D deficiency can reduce hospitalized bronchiectasis exacerbation occurrence.

6. Subject recruitment

A prospective self-controlled study will be conducted to assess the potential benefits of vitamin D supplementation, aiming at raising the blood 25-hydroxyvitamin-D level above 50 nmol/L.

This study will be conducted at the Department of Medicine, Queen Mary Hospital. The Division of Respiratory Medicine at Queen Mary Hospital is a tertiary referral centre serving the entire territory and is the major receiving unit for patients with various respiratory diseases (including bronchiectasis) in the Hong Kong West Cluster.

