Patients who participated in the prior study entitled “Prospective clinical study on serum 25-hydroxyvitamin D (25-OH D) level and risk of bronchiectasis exacerbation” (UW 22-317) will be invited for participation during regular clinic follow-up and management in Queen Mary Hospital. If they are willing to join the further research, they will be recruited in this self-controlled study. There were 104 subjects in the aforementioned study who will be separated into two groups according to their Baseline blood 25-hydroxyvitamin-D level: vitamin D deficient (below 50 nmol/L) and vitamin D non-deficient (at or above 50 nmol/L). There were initially 42 and 62 patients in the vitamin D deficient and vitamin D non-deficient groups respectively. Patients would be rechecked for 25-hydroxyvitamin-D level to confirm the persistence of deficiency at the recruitment visit.

The following eligibility criteria will apply.

Inclusion criteria: Patients with

1. ages 18 years or above, male or female.
2. confirmed diagnosis of non-CF bronchiectasis based on high-resolution computed tomography (HRCT) scan.
3. participation in the prior study entitled “Prospective clinical study on serum 25-hydroxyvitamin D (25-OH D) level and risk of bronchiectasis exacerbation” (UW 22-317)

Exclusion criteria: Patients with

1. underlying asthma, COPD and other co-existing respiratory diseases
2. underlying osteoporosis
3. supplementary Vitamin D in their regimen
4. advanced chronic kidney disease with estimated glomerular filtration rate (eGFR) < 30mL/min

7. Brief outline of methodology

The following will be performed at the recruitment visit: Detailed medical history (Demographics, duration of bronchiectasis, co-morbidities, exacerbation history), questionnaires (SGRQ, Modified Medical Research Council (mMRC) dyspnoea scale, bronchiectasis impact measure (BIM), Bronchiectasis Health Questionnaire (BHQ)), physical examination, blood tests (Complete blood count, liver and renal function test, 25-hydroxyvitamin-D level, calcium and phosphate level, erythrocyte sedimentation rate, C-reactive protein, high-sensitivity C-reactive protein), and sputum analysis (Bacterial smear and culture, acid fast bacilli smear and culture). The detailed study procedures are summarized in Table 1. The estimated duration for each visit would be 15 minutes.

Outcome measurement

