The primary outcome measure is the proportion of patients who develop hospitalized bronchiectasis exacerbation during the follow-up period of 12 months, when compared with the 1-year period before. The Vitamin D deficient group will be compared with their historical data collected in the prior study entitled “Prospective clinical study on serum 25-hydroxyvitamin D (25-OH D) level and risk of bronchiectasis exacerbation” (UW 22-317) as self-control, as well as the vitamin D non-deficient group.

The secondary outcomes include the change in SGRQ, BIM and BHQ score at 6 and 12 months from baseline, as well as change in number of all/hospitalized bronchiectasis exacerbation in the follow up period of 12 months.

Those with vitamin D deficiency will be replaced with vitamin D3 at 1000 IU at the first visit. Vitamin D3 1000 IU is expected to increase blood 25-hydroxyvitamin-D level by 25 nmol/L. Blood 25-hydroxyvitamin-D level will be rechecked 3 months after replacement. If the blood 25-hydroxyvitamin-D level is still below 50 nmol/L, the vitamin D3 replacement dosage will be increased to 2000 IU. Blood 25-hydroxyvitamin-D level will be checked again at 6 and 12 months.

Patients will be followed up at 3, 6 and 12 months after recruitment. Except for the sputum analysis and blood tests, the same measures in Table 1 will be performed at 6 and 12 months. In addition, patients will be assessed on their bronchiectasis exacerbation record (both bronchiectasis exacerbation managed in an out-patient setting and hospitalized bronchiectasis exacerbation).

Methods

Blood 25-hydroxyvitamin-D level

25-hydroxyvitamin-D will be measured in nmol/L, using in-house liquid chromatography with tandem mass spectrometry (LC/MS-MS) developed by the Department of Chemical Pathology of Queen Mary Hospital. Vitamin D deficiency is defined as 25-hydroxyvitamin-D level below 50 nmol/L, while sufficient vitamin D level is defined as above 50 nmol/L, per the Endocrine Society guidelines (32, 33).

Bronchiectasis exacerbation

Bronchiectasis exacerbation was defined as [1] a deterioration in three or more of the following key symptoms for at least 48 hours, including cough, sputum volume and/or consistency, sputum purulence, dyspnea and/or exercise tolerance, fatigue and/or malaise, hemoptysis AND [2] clinician assessment that a change in bronchiectasis treatment was required usually with administration of antibiotics treatment.

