Patients will be followed up at 3, 6 and 12 months after recruitment. Except for the sputum analysis and blood tests, the same measures in Table 1 will be performed at 6 and 12 months. In addition, patients will be assessed on their bronchiectasis exacerbation record (both bronchiectasis exacerbation managed in an out-patient setting and hospitalized bronchiectasis exacerbation).

Subjects (with justification on the sample size)

Patients who participated in the prior study entitled “Prospective clinical study on serum 25-hydroxyvitamin D (25-OH D) level and risk of bronchiectasis exacerbation” (UW 22-317) will be recruited in this self-controlled study.

There were 104 subjects in the aforementioned study who will be separated into two groups according to their Baseline blood 25-hydroxyvitamin-D level: vitamin D deficient (below 50 nmol/L) and vitamin D non-deficient (at or above 50 nmol/L). There were initially 42 and 62 patients in the vitamin D deficient and vitamin D non-deficient groups respectively.

Data processing and analysis

The demographic and clinical data will be described in actual frequency or mean \pm SD, or median and interquartile range, where appropriate.

Baseline demographic and clinical data will be tabulated, as well as compared between Vitamin D deficient and vitamin D non-deficient groups by independent t-test or non-parametric tests where appropriate.

In the Vitamin D deficient group, the proportion of patients with hospitalized bronchiectasis exacerbation before and after vitamin D replacement will be compared by binary logistic regression. The number of all/hospitalized bronchiectasis exacerbation before and after vitamin D replacement will be compared by will be compared with linear regression.

The proportion of patients with all/hospitalized bronchiectasis exacerbation and between vitamin D deficient and vitamin D non-deficient groups will be compared by binary logistic regression. The number of all/hospitalized bronchiectasis exacerbation between vitamin D deficient and vitamin D non-deficient groups will be compared by will be compared with linear regression.

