Covariates including FACED score, age, gender and smoking status will be adjusted in multivariate analysis. For secondary outcome, the change in SGRQ, BIM and BHQ scores at the end of study will be compared between the two groups by linear regression and adjusted for confounders in multivariate analysis. A p-value of <0.05 will be considered statistically significant. All the statistical analyses will be performed using the latest version of Statistical Package for the Social Sciences (SPSS) software.

8. Potential hazards to subjects in the study

Patients will undergo blood tests and breathing (lung function) tests. The breathing tests may be associated with some discomfort, such as chest soreness, shortness of breath and lightheadedness. Pain, bruising or infection may occur from the needle puncture sites. Should patients' non-CF bronchiectasis significantly worsen in the course of the study, study doctor will withdraw them from the study and provide appropriate medical treatment.

Over-replacement of Vitamin D may lead to Vitamin D toxicity which can have the following symptoms: nausea, vomiting, loss of appetite, constipation, dehydration, fatigue, irritability, confusion, weakness and/or weight loss. In this study, the blood serum 25(OH)D level will be checked before the start of Vitamin D replacement and at 3 months after replacement, to ensure the replacement is adequate but not excessive.

9. Confidentiality and use of results

The demographic and clinical data collected from study subjects will be stored securely at the study site for 5 years, with access by the principal investigator or his designated research staff. These data will only be used for the study as outlined in this protocol and individual patient's identity will be removed after completion of statistical analyses.

10. Personal experience of the investigators in the field

The Division of Respiratory Medicine has a strong track record in conducting clinical research on bronchiectasis. Queen Mary Hospital is a well-recognised tertiary referral and research centre in the field of respiratory medicine, with numerous research on bronchiectasis and respiratory diseases conducted therein during the past years. All the investigators are experienced and accredited specialist. Within the last 3 years, the PI ([name]) has served as the first author of 9 out of 10 publications on bronchiectasis.

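### The before/after primary comparison is paired, but the protocol names plain binary logistic regression, which ignores the pairing and gives too large a standard error if within-patient correlation is positive

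*Protocol*

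**What the plan says.** Section 6 (Subject recruitment) sets the design: "A prospective self-controlled study will be conducted to assess the potential benefits of vitamin D supplementation". Section 7, Outcome measurement, defines the primary outcome as the proportion of patients with a hospitalized exacerbation "during the follow-up period of 12 months, when compared with the 1-year period before", and adds: "The Vitamin D deficient group will be compared with their historical data collected in the prior study". Each deficient patient therefore supplies one yes/no result for the year before and one for the year after.

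Section 7, Data processing and analysis, fixes the method for this contrast: "the proportion of patients with hospitalized bronchiectasis exacerbation before and after vitamin D replacement will be compared by binary logistic regression". The next paragraph gives the same method for the other contrast, where proportions "between vitamin D deficient and vitamin D non-deficient groups will be compared by binary logistic regression". On adjustment it says: "Covariates including FACED score, age, gender and smoking status will be adjusted in multivariate analysis". No McNemar or conditional analysis, patient term, cluster, random effect or robust standard error is named anywhere in the protocol.

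**The concern.** The two contrasts have different data structures. Deficient and non-deficient patients are separate people, so ordinary logistic regression suits that comparison. The before and after results come from the same people, and a patient admitted in one year is plausibly more likely than others to be admitted in the next. Ordinary logistic regression takes the two results as unrelated. Unadjusted, its answer depends only on the two totals and not on which patients changed, so it discards the information that a self-controlled design exists to provide.

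This is the first-named contrast of the primary outcome. With positive within-patient correlation its confidence interval would be too wide and its p-value too large, in a study with at most 42 pairs.

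**Working it through.** **Inputs from the protocol.** There are at most 42 pairs (section 6 and the sample-size paragraph of section 7). Fewer are likely, because "Patients would be rechecked for 25-hydroxyvitamin-D level to confirm the persistence of deficiency at the recruitment visit" and the exclusions and consent also apply. Significance is p < 0.05, taken as two-sided. The protocol gives no power or sample-size figure for this contrast, so there is none to reproduce.

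**Inputs assumed.** The documents give neither r nor a one-year rate.

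- *r:* 0.1 to 0.5 is used. For 20% falling to 10% the ceiling is (0.10 − 0.20×0.10)/sqrt(0.16×0.09) = 0.08/0.12 = 0.67.
- *Before-rate:* section 3 reports, for hospitalized exacerbation at six months, "13.3% in vitamin D deficient group and 2.5% in vitamin D non-deficient group", but only 10% for any exacerbation in the deficient group. A subset cannot exceed the whole, so both are carried as a range. The 12-month rate is 2p − [p² + r·p(1−p)], with r = 0.3 between half-years. For p = 0.10 this is 0.20 − (0.010 + 0.027) = 16.3%; for p = 0.133 it is 0.266 − (0.0177 + 0.0346) = 21.4%. If no patient has events in both halves, the rates are 20% and 26.6%.

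**Standard error.** With v = p(1−p) for each period, ordinary SE / correct SE = sqrt(v1+v2) / sqrt(v1+v2−2r·sqrt(v1·v2)). When v1 = v2 this is 1/sqrt(1−r), whatever the rate: 1.05, 1.12, 1.20 and 1.41 at r = 0.1, 0.2, 0.3 and 0.5.

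**Size and power.** These come from exact enumeration of the four-cell paired table. A period with no events counts as no rejection for the Wald tests. LR is the likelihood-ratio test.

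| 42 pairs | Ordinary Wald | Ordinary LR | Mid-p McNemar | GEE by patient |
|---|---|---|---|---|
| Size, 20% both years, r=0.1 | 3.2% | 4.1% | 4.3% | 4.5% |
| Size, r=0.3 | 1.5% | 2.1% | 4.1% | 4.4% |
| Size, r=0.5 | 0.4% | 0.7% | 3.4% | 4.6% |
| Power, 20% to 10%, r=0.1 | 18.2% | 24.8% | 23.9% | 22.3% |
| Power, r=0.3 | 15.2% | 22.0% | 28.5% | 28.5% |
| Power, r=0.5 | 11.5% | 18.2% | 34.8% | 40.5% |

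With the other before-rates halved (42 pairs, r = 0.3), LR against mid-p is 18.0% v 21.4% (from 16.3%), 23.7% v 31.1% (from 21.4%) and 31.0% v 40.6% (from 26.6%). With 30 pairs and 20% to 10%, it is 20.2% v 16.3% at r = 0.1, 17.3% v 17.7% at 0.3 and 13.6% v 18.5% at 0.5.

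**Worked table.** Suppose 9 of 42 have an event before and 3 of 42 after. The log odds ratio is ln[(9/33)/(3/39)] = 1.27, with ordinary SE sqrt(1/9+1/33+1/3+1/39) = 0.707. Wald p = 0.074 and LR p = 0.056, however the events are paired. The paired answers differ:

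| Patients with events in both years | Discordant pairs | r | Mid-p | GEE SE |
|---|---|---|---|---|
| 0 | 9, 3 | −0.14 | 0.092 | 0.752 |
| 1 | 8, 2 | 0.08 | 0.065 | 0.681 |
| 2 | 7, 1 | 0.31 | 0.039 | 0.602 |
| 3 | 6, 0 | 0.53 | 0.016 | 0.511 |

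Identical totals fall on either side of 0.05 depending on which patients changed, and ordinary logistic regression cannot see this.

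**The case against.** The protocol does not use the word ordinary. Binary logistic regression could cover a conditional or repeated-records fit, and a SAP not shown here might specify one. That is possible. However, the identical wording for the independent-group contrast and a covariate list without a patient term make the unpaired model the plain reading. The protocol names a method that does not fit, so this is not a detail merely left for later.

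The stronger objection concerns weight, and much of it stands. The error is conservative and arises only if r is positive. At r = 0.1 almost nothing changes: LR size is 4.1% against 4.3% for mid-p. Pairing can even cost power. At 30 pairs and r = 0.1, LR has 20.2% and mid-p 16.3%; with 16.3% halved and r = 0.3, the figures are 14.6% and 12.2%. Exact McNemar is below LR even at 42 pairs and r = 0.3 (19.4% v 22.0%). Power is low under every method shown, so pairing does not rescue a small pilot.

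The figures are also unadjusted. FACED score, age, gender and smoking status would absorb some of the correlation, so the effect on the adjusted model may be smaller. They remove only the part that they explain.

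Finally, McNemar cannot carry those covariates, so naming it alone would conflict with the planned adjustment. The fix has to cover both analyses.

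**Conclusion.** The concern holds: as written, the method does not match the paired design of the before/after primary contrast. With positive r the standard error is overstated by about 1/sqrt(1−r) under no change, that is 5% to 41% for r from 0.1 to 0.5, and the test rejects too rarely. This result does not depend on the event rate. It does depend on r, which is assumed, and on the unadjusted model; at r = 0 there is no error, and at negative r the standard error would be too small.

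For positive r, false positives are not inflated, the unadjusted odds ratio is still a valid marginal estimate, and the deficient v non-deficient comparison is unaffected. The case rests on a standard error and interval that fit the design, not on a promised gain in power. The point should be fixed but does not undermine the study.

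**What to change.** In Data processing and analysis, replace the sentence on before and after proportions with, for example: *In the vitamin D deficient group, the proportions with hospitalized exacerbation in the year before and the year after replacement will be compared by a paired analysis (mid-p McNemar test), with the paired risk difference and a 95% confidence interval suited to small paired samples. The covariate-adjusted comparison will use a logistic model that accounts for two records per patient (GEE or mixed model by patient).*

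Mid-p McNemar is one suitable choice; another paired or clustered analysis would also correct the error. Patient-fixed covariates can enter a GEE or mixed model but drop out of McNemar or conditional analyses. Keep ordinary logistic regression for deficient v non-deficient patients. The next sentence of the protocol, which compares before and after exacerbation counts by linear regression, has the same pairing problem and should be revised at the same time.

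The cost is a sentence or two and no new data. The mid-p value needs only the two discordant counts. Check that the chosen adjusted model can be run in SPSS, the only software named.

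### Exacerbation counts are compared by plain linear regression: no pairing is stated before/after, and there is no provision for unequal variances between the groups of 42 and 62

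*Protocol*

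**What the plan says.** Section 7, Outcome measurement, lists among the secondary outcomes the "change in number of all/hospitalized bronchiectasis exacerbation in the follow up period of 12 months". For the primary outcome it sets up two comparisons: "The Vitamin D deficient group will be compared with their historical data collected in the prior study entitled" (the earlier study), and the deficient against the non-deficient group. Section 6 and the sample-size paragraph of section 7 call the study self-controlled; patients of the earlier study "will be recruited in this self-controlled study".

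The analysis is fixed in section 7, Data processing and analysis. Within the deficient group: "The number of all/hospitalized bronchiectasis exacerbation before and after vitamin D replacement will be compared by will be compared with linear regression". For the second comparison, the number of events "between vitamin D deficient and vitamin D non-deficient groups will be compared by will be compared with linear regression". On adjustment: "Covariates including FACED score, age, gender and smoking status will be adjusted in multivariate analysis". For the questionnaires the same section does name a change score: "the change in SGRQ, BIM and BHQ scores at the end of study will be compared between the two groups by linear regression". For the counts it names no change score, patient term or variance option.

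Group sizes are given as initially 42 deficient and 62 non-deficient. The protocol gives no mean, SD or within-patient correlation for the counts.

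**The concern.** Two features of plain linear regression matter here, and they act in opposite directions.

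- **Before/after.** Two counts from one patient are correlated. A regression of count on period, with each patient-year as a separate row, ignores this and gives a standard error (SE) that is too large. The self-controlled design would then lose its main advantage.
- **Between groups.** Ordinary linear regression assumes one common variance, while the variance of a count rises with its mean. If the smaller group has the higher rate, pooling understates the SE and the confidence interval is too narrow. Section 3 reports a higher hospitalized rate in the smaller, deficient group.

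The main product of a pilot is an estimate with an honest interval, so both points bear on what the study can report. They concern secondary outcomes only.

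**Working it through.** The plan has no figure of its own for the counts, so there is nothing to reproduce. The sizes below rest on assumed rates.

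**Step 1: rates from section 3.** "There were 70 patients who completed the interim analysis at 6 months". The reported percentages are 13.3% v 2.5% (hospitalized) and 10% v 0% (exacerbation). The only integer split of 70 that gives 13.3%, 10.0% and 2.5% is 30 deficient and 40 non-deficient, with 4, 3 and 1 patients. As yearly Poisson rates, −2·ln(1−p):
- 4/30: −2·ln(0.8667) = 0.286
- 1/40: −2·ln(0.975) = 0.051

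The exact 95% intervals are 0.08-0.73 and 0.001-0.28.

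**Step 2: are these rates safe?** No, for two reasons. Hospitalized events are by definition a subset of exacerbations, yet more patients are reported with the former. Also, the uncorrected chi-square gives p = 0.082 for 4/30 v 1/40 and p = 0.041 for 3/30 v 0/40, while section 3 prints 0.041 for hospitalized and 0.082 for exacerbation. The p-values fit the opposite endpoints, so hospitalized events may have been 3 v 0. The rates serve only as illustration.

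**Step 3: before/after.** Counts are Poisson given a patient-specific gamma rate, with mean m and dispersion k. With no effect, the within-patient correlation is ρ = km/(1+km), so unpaired SE / paired SE = 1/√(1−ρ) = √(1+km):
- m = 0.286, k = 0.5: √1.143 = 1.07
- m = 0.286, k = 3: √1.858 = 1.36
- m = 2, k = 0.5: √2 = 1.41

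Simulated power for a true halving, n = 42 (the most available), two-sided 5%:

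| Rate/year | k | Unpaired | Paired |
|---|---|---|---|
| 0.08 | 0.5 | 9% | 8% |
| 0.286 | 0.5 | 24% | 26% |
| 0.286 | 1 | 21% | 26% |
| 0.286 | 3 | 12% | 22% |
| 0.73 | 0.5 | 50% | 58% |
| 0.73 | 3 | 16% | 50% |
| 2 | 0.5 | 86% | 95% |

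The last row matches the registry figure in section 3: with m = 2 and k = 0.5, P(0) = P(1) = 0.25, so half the patients have two or more. With no effect, the unpaired test rejects less often than 5% (1.6-4.4% at means of 0.133-0.266, below 2% at means of 1-2), so there is no excess of false positives.

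**Step 4: between groups, 42 v 62.** With v = m + km²:
- pooled variance = (41·v1 + 61·v2)/102
- equal-variance SE = √[pooled·(1/42 + 1/62)]
- true SE = √(v1/42 + v2/62)

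Example, Poisson, 0.286 v 0.051: pooled = (41·0.286 + 61·0.051)/102 = 0.1455. Equal-variance SE = √(0.1455·0.03994) = 0.0762. True SE = √(0.00681 + 0.00082) = 0.0874. Ratio 0.87.

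| Deficient v other | Rate ratio | SE ratio, k = 0 to 3 |
|---|---|---|
| 0.286 v 0.051 | 5.6 | 0.87-0.85 |
| 0.143 v 0.051 | 2.8 | 0.91-0.90 |
| 0.102 v 0.051 | 2.0 | 0.94-0.93 |
| 0.077 v 0.051 | 1.5 | 0.96 |
| 0.051 v 0.051 | 1.0 | 1.00 |
| 0.0255 v 0.051 | 0.5 | 1.07 |

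At 0.286 v 0.051 the nominal 95% interval covers about 87-90% with equal variance and about 90-93% with unequal variances. At 0.143 v 0.051 the figures are 91-92% and 92-94%. Part of the shortfall is therefore skewness from few events, which a better SE does not cure. At equal rates the test rejects in 4.5-5.0% of runs.

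**The case against.** The best defence of the before/after analysis is that the outcome is already defined as a change in number, in a study that calls itself self-controlled. Linear regression on one change per patient fits that definition and loses nothing, and such model detail often sits in a statistical analysis plan. Much of this stands: the protocol permits the paired reading, and a claim that the plan discards the pairing would go too far. What remains is that the analysis section names a method for the counts without carrying the change through, although it does so for the questionnaires. Two analysts could follow it and report different intervals.

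On the between-group half, the defence is that the shortfall depends on a large rate difference, which the trial hopes to shrink. That also stands. A reader might infer that the SE is 9-15% too small whenever the deficient group keeps the higher rate. The documents do not support this: at ratios of 1.5-2 the shortfall is 4-7%, and the direction reverses if the deficient rate ends lower.

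A further defence is that a count model is no cure. If one group has no hospitalized events, a rate ratio cannot be estimated. This happens in about 5% of simulated trials at 0.286 v 0.051, in 16-18% if both groups are at 0.051, and it is what 3 v 0 in the interim data would look like. This is a sound reason not to make the rate ratio the main result.

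**Conclusion.** The point holds as a minor one. The protocol names plain linear regression for sparse counts in both comparisons, without stated pairing or a variance provision, and a better choice costs almost nothing.

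Before/after, the harm arises only if the two years are analysed as independent rows. It is then lost precision: slight at low rates and low dispersion, substantial at higher ones. Between groups, the SE is about 4-7% too small at rate ratios of 1.5-2 and 9-15% too small from about 2.8 upwards, correct at equal rates, and about 7% too large if the deficient rate is half the other.

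A reader might infer that linear regression inflates false positives here. It does not: the unpaired test is conservative, and the between-group test keeps its size at equal rates. The between-group fault is in interval coverage when rates differ.

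The sizes assume gamma-Poisson counts, a true halving for the power figures, full groups of 42 and 62, and no covariate adjustment. They lean on interim rates that section 3 itself makes doubtful, so they should be read as ranges.

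**What to change.** In section 7, Data processing and analysis:

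1. **Before/after.** State that the count comparison is paired. Make the within-patient mean change with its 95% interval the main analysis (paired t, or regression on one change per patient). In simulation at n = 42 the paired t-test had 4-5% type I error and its interval covered 93-95%.
2. **Between groups.** Report the mean difference with an unequal-variance SE (a robust SE where covariates are included) as the main result. Add a Poisson or negative binomial rate ratio with robust SEs and log follow-up time as offset, as a supporting analysis when both groups have events.

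Adjusting for the prior-year count is optional. It does not make the between-group contrast a treatment effect: in simulation with no effect, a rate ratio of 5.6 fell only to 3.6-5.1 after adjustment.

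The cost is a few sentences and slightly more analysis work; no extra patients, visits or data are needed. Two limits remain: the part of the coverage shortfall that comes from skewness, and any bias from withdrawing patients who worsen (section 8), which neither the paired change nor the offset removes.
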